11.4 Study Variables and Methods of Assessment

11.4.1 Efficacy Variables

11.4.1.1 Overview of Efficacy Variables

The primary and some secondary efficacy variables are derived from the 4-hour pH monitoring sessions following four Compound Sodium Alginate Double Action Chewable Tablets or four matching placebo tablets.

11.4.1.2 Methods of Assessment of Efficacy Variables

Efficacy is assessed by esophageal pH monitoring following a standard refluxogenic test meal. A single dose of the study treatment is administered 30 minutes after completion of the meal and pH measurements recorded for 4 hours post-dose. Patients will be randomised to receive four Compound Sodium Alginate Double Action Chewable Tablets or four matching placebo tablets and one week later will receive the alternate treatment.

11.4.2 Appropriateness of Measurements

Esophageal pH monitoring is a well validated and accepted technique for diagnosis of gastro-esophageal reflux disease (GERD). It provides direct physiologic measurement of acid in the esophagus and can assess the response of the disease to treatment. In this study it is being used to assess and compare the effects of four Compound Sodium Alginate Double Action Chewable Tablets and four matching placebo tablets on pH over a 4 hour post-dose period 30 minutes after a refluxogenic meal.

A crossover design is used for this study where the patient has pH measurement after Compound Sodium Alginate Double Action Chewable Tablets and matching placebo tablets on two separate occasions. A 7-day washout period occurs between each pH monitoring visit; all patients will receive standard treatment, Compound Sodium Alginate Double Action Chewable Tablets (two tablets four times daily), for their symptoms of GERD during this washout period between pH monitoring visits.

11.5 Study Specific Supplies

Not applicable

11.6 Unscheduled Visits

If unscheduled visits occur, the Investigator must record the following in the patient's CRF:

- Reason for unscheduled visit
- Any AEs.
- Concomitant therapy changes.
- Withdrawal (if deemed appropriate).
- Any clinical assessments deemed appropriate for the clinical care of the patient.

If the dosage regimen of study medication has been changed, the Investigator must contact the RB Clinical Project Manager in order to determine if the patient should be withdrawn from the study or may be allowed to continue. The Clinical Project Manager will advise the Investigator of how information should be recorded on the CRF.

Unscheduled visits should not alter the timing of the routine study schedule.

11.7 Patient Withdrawal and Replacement Criteria

11.7.1 Patient Withdrawal

The Investigator may withdraw the patient from the study at any time. Reasons for removing a patient from the study include, but are not limited to:

- AEs that in the judgement of the Investigator may cause severe or permanent harm (significant clinical deterioration is an AE).
- Violation of the study protocol.
- In the Investigator's judgement, it is in the patient's best interest.

- Patient declines further study participation.

The primary reason for withdrawal will be documented as one of the following: AE; lack of efficacy; lost to follow-up; no further need for IMP (unless this is a study endpoint); protocol violation; death; withdrawal of consent; other. The Investigator must make reasonable attempts to contact patients who are lost to follow-up - a minimum of 2 documented telephone calls or a letter is considered reasonable.

In the event of early withdrawal the patient should have the assessments listed in Section 11.3.2.3 completed.

11.7.2 Replacement of Patients

Patients who withdraw from the study will not be replaced.

11.8 Additional Care of Study Patients Following Completion of the Study

Patients who experience AEs at the end of the study, or experience the onset of an AE after the end of the study, will be followed up as described in Sections 13.1.7 and 13.1.8.

No other additional care of study patients will take place following the end of the study. The treatment of the patient's condition will follow normal clinical practice.

11.9 Treatment Compliance

The IMP will be administered at the study site under the supervision of the Investigator or his or her delegate.

11.10 Premature Termination of the Study

RB may prematurely terminate the conduct of the study specific study sites or the entire study. Reasons for early termination include, but are not limited to:

- Inability to recruit or slow recruitment of patients

- Unacceptable data quality
- Concerns regarding the risk/benefit ratio
- Withdrawal of CA or IEC approval
- Recall of a batch of IMP where replacement medication will not be provided
- Results from an interim statistical or safety analysis
- Inability to remedy a clinical hold or suspension
- Unresolved non-compliance with GCP or the protocol that compromises patient rights or safety or the study data

The CPM will inform all investigators in writing at specific study sites relevant to the decision. A suitable course of action will be agreed for existing patients. The investigator will inform the IEC/IRB in writing and provide a copy to RB for filing in the TMF. [REDACTED] will inform the SFDA within 15 days of the date of termination and file a copy of the correspondence in TMF.

12 STUDY TREATMENTS

12.1 Identity of Investigational Medicinal Products

The following medication will be supplied.

- Compound Sodium Alginate Double Action Chewable Tablets.
- Matching placebo tablets.

Compound Sodium Alginate Double Action Chewable Tablets will be manufactured to Good Manufacturing Practice (GMP) by Reckitt Benckiser Healthcare (UK) Limited, [name], UK (Product Licence 00063/0157). The matching placebo tablets will be manufactured to Good Manufacturing Practice (GMP) by [REDACTED]
[REDACTED] for RB.

The active and placebo treatment will be shipped to [REDACTED]
[REDACTED] where both active and placebo will be blister packed. The blister packs will be shipped to the Investigational Material Supplies Unit (IMSU), Reckitt Benckiser Healthcare UK Ltd, [name] UK.

The supplies will be assembled and labelled to GMP standards by the Investigational Material Supplies Unit (IMSU), Reckitt Benckiser Healthcare UK Ltd, [name]. They will be shipped directly from IMSU to be distributed to the investigator sites from a distribution centre in China.

For the open-label single dose treatments, labels will identify which of the two treatments (active or placebo) the patient's pack contains.

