12.3 Randomisation and Treatment Allocation

12.3.1 Randomisation

Drug supplies for the two single doses per patient will be randomised by the RB IMSU, according to a computer-produced randomisation schedule. On randomisation, patients will be allocated a unique patient number in numerical sequence. Issue of the IMP in this sequence will ensure randomisation.

The IMSU will hold the master code for the randomisation schedule.

This study is not blinded.

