12.3.2 Blinding

This study is not blinded.

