12.6 Packaging

Sufficient drug supplies will be packaged and labelled for 100 patients for the single dose crossover.

Each patient's open-label, single dose pack will contain two blister packs each pack containing 4 tablets. Four tablets are to be taken from the first blister pack at the first pH monitoring visit and four tablets are to be taken from the second blister pack at the second pH monitoring visit.

Each patient's complete pack for the study will consist of:

- One blister pack containing 4 Compound Sodium Alginate Double Action Chewable Tablets
- One blister pack containing 4 matching placebo tablets

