5. ANALYSIS SETS

Agreement and authorization of patients included/excluded from each analysis set will be conducted at data review meeting before database lock.

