5.4. PER PROTOCOL [PP] POPULATION

The inclusion/exclusion from per protocol (PP) population will be confirmed during data review meeting, but will include patients who satisfied following criteria and did not experience any major protocol violations in ITT population: patients who adhered to the inclusive/exclusive criteria; did not take any prohibited medication which would interfere with evaluation of drugs in the study period; attended visits within the specified visit windows and had complete pH monitoring data for 4 hour post-dosing for both pH monitoring visits.

A major violation of the protocol is defined as any violation of the protocol that is considered to affect the efficacy results and may include the following:

- When a randomization error or administration of the wrong study medication occurred;
- When the patient did not satisfy the inclusion/exclusion criteria;
- When the patient had taken prohibited concomitant medications;
- When the patient failed to attend visit at specified visit windows;
- When the efficacy (4 hour post-dosing monitoring) evaluation was not completed for either monitoring visits.

Protocol violations will be categorized before database lock and will be summarized (by treatment sequence group and overall) and listed.

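### A matching placebo is supplied, but the packs name the treatment, no reason is given, and no masking is required when evaluable traces and analysis sets are decided

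*Protocol*

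**What the plan says.** **Supplies.** Protocol 12.1 describes active and matching placebo tablets sent to a packing site "where both active and placebo will be blister packed", then assembled and labelled by the sponsor's supplies unit. For the single doses, "labels will identify which of the two treatments (active or placebo") the pack holds. Each patient's pack holds one active blister and "One blister pack containing 4 matching placebo tablets" (Protocol 12.6). The supplies unit randomises the supplies from a computer-produced schedule and holds the master code (Protocol 12.3.1).

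**Blinding.** Protocol 12.3.2 says "This study is not blinded", and 12.3.1 and 12.3.3 say the same. Protocol 9.3 defends pH monitoring and the crossover but does not discuss open label. Protocol 13.1.5 still restricts breaking the randomisation code, and refers for this to Section 12.2, which covers the non-investigational product.

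**Analysis sets.** ITT entry needs one dose and at least 1 hour of evaluable post-dose pH data (Protocol 14.2; SAP 5.3). *Evaluable* is not defined. For the PP set, "A major violation of the protocol is defined as any violation of the protocol that is considered to affect the efficacy results", followed by a list introduced as possible examples (SAP 5.4). SAP 5 adds: "Agreement and authorization of patients included/excluded from each analysis set will be conducted at data review meeting before database lock". SAP 4 requires the sponsor to authorise the sets. None of these sections mentions masking.

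**The concern.** The aim is statistically significant superiority over placebo (Protocol 8), as evidence for regulatory applications (Protocol 6). A trial that already pays for a matching placebo would normally use it to mask the people who run the session and judge the data. Here the label gives that up without a stated reason, and the SAP does not restore masking at the later steps where it would still be possible.

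A data logger reads the endpoint, but people decide when recording stops, whether a trace is evaluable and who belongs in each set. If those decisions lean even slightly with knowledge of treatment, the contrast shifts. The PP and complete-case analyses (SAP 15.1.4) would not reveal a shift that arises in the session, because they use the same traces.

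**Working it through.** The plan gives no figure for this point. Protocol 14.1 states that the sample size has no statistical justification, so there is no effect size, SD or power to reproduce. The check is mainly textual, with one illustrative calculation.

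**Step 1. Who can know the treatment, and when.**

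| Step | What the documents establish |
|---|---|
| Electrode placement, Visit 2 | Unclear. Protocol 8 puts randomisation 30 minutes after the meal, hence after placement. Protocol 11.3.2.1 lists number allocation and dispensing before the pH procedure. |
| Electrode placement, Visit 3 | Treatment known: it is the alternate of the Visit 2 treatment (Protocol 11.3.2.2). |
| Supervision from dosing to 4 hours, both visits | Treatment known from the label (Protocol 12.1). |
| Evaluable data (ITT entry) | Criterion undefined; no masking required (Protocol 14.2; SAP 5.3). |
| Major violations | Open-ended list; PP set only (SAP 5.4). |
| Agreement of analysis sets | Before lock; nothing said about masking (SAP 5). |

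**Step 2. What already limits bias.**

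- Placement follows manometry, 5 cm above the lower sphincter, and the trace goes to a data logger (Protocol 11.3.2.1).
- The primary variable is missing below 2 hours of recording (SAP 15.1.2). This is a duration rule and leaves little to judgement. It applies whatever the reason for stopping, however. The 230-minute example in the SAP table leaves the percentage at 80.0%, so a shortened trace stands for the full 4 hours.
- Each patient receives both treatments, and visit and sequence are in the model (SAP 15.1.3).
- ITT is the primary efficacy population (Protocol 14.2), so PP decisions do not alter the primary result.

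**Step 3. Illustration of size.**

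Inputs from the documents: 36 evaluable patients (Protocol 14.1) and a two-sided 5% test (Protocol 14.4.3). Assumptions: 18 patients per sequence, normal within-patient differences, and a constant bias *b* in SDs of the within-patient difference, with no true treatment effect.

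- Degrees of freedom = 36 − 2 = 34; critical value about 2.03.
- Noncentrality = *b* × √36 = 6*b*.
- Rejection rate = P(|T| > 2.03), T noncentral t with 34 df.

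| *b* (SD) | 6*b* | Rejection rate |
|---|---|---|
| 0 | 0 | 5.0% |
| 0.05 | 0.3 | 6.0% |
| 0.10 | 0.6 | 9.0% |
| 0.20 | 1.2 | 21% |

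For scale, 36 patients give 80% power for a true difference of 0.48 SD, so a bias of 0.1 SD is about a fifth of that (0.1/0.48 = 0.21). The documents give no basis for choosing any row, nor for the direction of a bias.

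**The case against.** The strongest defence is that open label is declared consistently, the endpoint is instrument-read, the main handling steps have written rules, and each patient is his or her own control. That stands as mitigation. It does not explain why the treatment is printed on the label, and it does not cover judgements about evaluable traces.

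A reader might infer more than the documents support:

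- **That electrode placement is unmasked at both visits.** This is established only for Visit 3. For Visit 2 the protocol conflicts with itself on when randomisation happens.
- **That the data review is carried out unmasked.** The SAP is silent. Masked listings are possible even with open site labels, so this is a separate gap in the SAP and not a consequence of the label.
- **That the open list of major violations can move the primary result.** It governs the PP set only. For the ITT set, the remaining gap is the undefined word *evaluable*.
- **That staff can steer the result by reading the next sequence.** Packs are used in number order ("Issue of the IMP in this sequence will ensure randomisation", Protocol 12.3.1) and carry treatment labels, so foresight of the sequence is plausible. In a crossover, choosing who gets which order favours neither treatment as it could in parallel groups.
- **That open label brings no benefit.** The documents do not say whether the placebo matches in taste or chewing feel. All patients are instructed to take active tablets between visits (Protocol 12.2). If taste differs, patients, and the staff supervising them, could recognise the Visit 3 dose and deduce the Visit 2 dose. Whether full masking was feasible cannot be judged.

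**Conclusion.** The point holds as an avoidable weakness with a cheap remedy. A matching placebo exists, the labels name the treatment, no reason is recorded, and no section requires masking when evaluability and analysis sets are decided. Site staff know the treatment during the post-dose session at both visits, and before electrode placement at Visit 3.

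The existing safeguards make a large bias less likely, but they do not exclude one. The error rates of 6% to 21% show only how sensitive a 36-patient crossover is to a systematic shift of 0.05 to 0.2 SD. They should not be read as an estimate of inflation in this trial. The documents do not show that bias occurred or that open label was without purpose.

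**What to change.** **(a) In the SAP, whatever is done about labels.** In sections 5, 5.3 and 5.4, define *evaluable* by objective criteria, such as minutes of usable post-dose signal and technical faults. Require that evaluability, protocol violations and ITT/PP membership be fixed before database lock from listings that hide treatment, sequence and pH results. Recording duration and visit can stay visible. Wrong-medication and randomisation errors, which SAP 5.4 counts as major violations, can be passed to the meeting as a yes/no flag by someone outside it. Cost: SAP wording and a set of masked listings.

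**(b) In the protocol, while supplies can still be labelled.** Label the two single-dose blisters by visit and randomisation number only. Keep the code in the supplies unit with a code-break procedure. Align 12.1, 12.3.2, 12.3.3 and 13.1.5, including its reference to Section 12.2, and the open-label descriptions elsewhere. Reconcile Sections 8 and 11.3.2.1 on when randomisation takes place. Cost: new label text, a code-break arrangement and an amendment. If the placebo does not match in taste, masking under (b) may be incomplete; the protocol should say whether it matches.

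Neither change alters treatment or sample size.

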12.3 Randomisation and Treatment Allocation

12.3.1 Randomisation

Drug supplies for the two single doses per patient will be randomised by the RB IMSU, according to a computer-produced randomisation schedule. On randomisation, patients will be allocated a unique patient number in numerical sequence. Issue of the IMP in this sequence will ensure randomisation.

The IMSU will hold the master code for the randomisation schedule.

This study is not blinded.

12.3.2 Blinding

This study is not blinded.

12.3.3 Emergency Unblinding Procedures

This study is not blinded.

12.3.4 IMP allocation for Replacement Patients

Patients will not be replaced.

12.4 Dosage Instructions

For the open-label, single dose treatment at each of the pH monitoring visits, patients will be administered four Compound Sodium Alginate Double Action Chewable Tablets or four matching placebo tablets.

All patients will be instructed by the Investigator on how they will take the medication, ie, thoroughly chew then swallow each tablet.

Medication errors may result in this study, from the administration or consumption of the wrong drug, by the wrong patient, at the wrong time, or at the wrong dosage strength. Such

medication errors occurring to a study participant will be captured on the adverse event (AE) page of the CRF and on a SAE form as appropriate. In the event of medication dosing error, the sponsor should be notified immediately.

Medication errors are reportable to RB irrespective of the presence of an associated AE/SAE, including:

- Medication errors involving patient exposure to a medicinal product
- Potential medication errors or uses outside of what is foreseen in the protocol that do or do not involve the participating patient.

Whether or not the medication error is accompanied by an AE/SAE, as determined by the investigator, the medication error and any associated AE/SAEs will be captured on an AE CRF page /SAE form (refer to Adverse Event Reporting section 13.1 for further details).

12.5 Standard Test Meal

In addition to the study medications, during the pH monitoring period, all the patients are required to consume a standard test meal on two separate occasions. This will comprise the following from McDonalds:

The Standardised Meal will consist of the following:

Medium sized McDonalds Big Mac

Portion of Medium size fries

Medium sized Fanta Orange Drink

This meal has a total calorific value of 990 kcal and contains protein 31 g, fat 40 g and carbohydrate 124 g.

12.6 Packaging

Sufficient drug supplies will be packaged and labelled for 100 patients for the single dose crossover.

Each patient's open-label, single dose pack will contain two blister packs each pack containing 4 tablets. Four tablets are to be taken from the first blister pack at the first pH monitoring visit and four tablets are to be taken from the second blister pack at the second pH monitoring visit.

Each patient's complete pack for the study will consist of:

- One blister pack containing 4 Compound Sodium Alginate Double Action Chewable Tablets
- One blister pack containing 4 matching placebo tablets

12.7 Labelling

12.7.1 Investigational Medicinal Product(s)

Supplied IMP(s) will be labelled according to GCP and GMP requirements and any other applicable national/state legislation.

Each patient pack and each patient carton will be labelled and each blister pack will be labelled.

12.7.2 Patient Carton

The blister packs containing the single dose study treatments will be contained in an outer carton.

12.7.3 Patient Pack

The patient pack will contain one open label treatment carton containing 8 blister packs of NIMP Compound Sodium Alginate Double Action Chewable Tablets and one single dose IMP carton containing the two single dose, open-label packs for to be administered at pH monitoring visits.

12.7.4 Non-Investigational Medicinal Products

Supplied NIMP will be labelled according to GCP and GMP requirements and any other applicable national/state legislation.

Each blister pack, patient pack and each patient carton will be labelled.

The patient will be asked to complete a NIMP return form noting the number of tablets returned.

12.8 Accountability of Investigational and Non-Investigational Medicinal Product(s)

The Investigator will keep all IMP(s) and NIMP(s) in a pharmacy or a secure storage facility, accessible only to those individuals authorised by the Investigator to dispense the medication.

The Investigator or designated individual will maintain an inventory. This will include the description and quantity of IMP(s) and NIMP(s) received during the course of this study, as well as a record of the materials that are dispensed and returned (how much, to whom, and when). This inventory ("Drug Dispensing Log") will be subject to review by the study monitor during monitoring visits.

The Investigator agrees not to supply IMP(s) and NIMP(s) to any person except study personnel and patients enrolled in this study.

All IMP(s) and NIMP(s) should be stored between 4°C and 30°C. Temperatures must be monitored using a minimum / maximum thermometer and recorded in a temperature log on working days.

12.9 Disposal of Unused Investigational and Non-Investigational Medicinal Product(s)

The Investigator agrees to conduct a drug supply inventory, to record the results of this inventory ("IMP/NIMP Removal from Site" form) and to return it and all original IMP/NIMP containers, whether empty or containing IMP or NIMP, to [REDACTED] at the end of the study or in stages during the course of the study.

[REDACTED] and RB will arrange for the appropriate and timely destruction of all returned IMP(s) and NIMP(s) following the end of the study (on finalisation of the study report).

12.10 Concomitant Therapies

Concomitant therapies are defined as prescribed medications, physical therapies, and over-the-counter preparations, including herbal preparations licensed for medicinal use, other than IMP(s) and NIMP(s) that the patient receives during the course of the study.

The Investigator will record any medications given for treatment of AEs on the concomitant medication page in the patient's CRF. Any medication taken by the patient from the time of giving informed consent through to the end of the study should also be recorded in the CRF. Any changes in concomitant therapy during the study will be documented, including cessation of therapy, initiation of therapy, and dose changes.

